Description of Study Intervention/Experimental Manipulation:	Describe the study intervention (a.k.a, experimental manipulation; hereafter referred to as “study intervention”). Include intervention dose (length and frequency) and how it will be administered. Include method of delivery (e.g., group vs. individual, web-based, etc.).
	Subjects enrolled will undergo surgical treatment of their kidney stones with URS based on clinician judgement and urologic guidelines. Once enrolled, patients will be randomized into one of two groups based on the type of laser used to break apart the stones: Thulium Laser or Hol:YAG Laser. Both lasers are used routinely and interchangeable for this procedure according to the standard of care. The only involvement of patients will be collection of urine samples before and after surgery.
Study Duration * :	Estimated time (in months) from when the study opens to enrollment until completion of data collection.
	12-18 months
Participant Duration:	Time (e.g., in months) it will take for each individual participant to complete all study-related tasks.
	10 days

1.2 SCHEMA

Patient eligibility will be confirmed during initial presentation of kidney stone, wherein [name] will determine if the patient is eligible to participate based on their clinical characteristics. [name] will determine if URS will be performed based upon available imaging studies and urologic standard of care. If so, [name] will explain the specifics of the study to the patient and ask if he or she is willing to participate. All patients will have pre- and postoperative urine samples collected which will be stored and analyzed for protein biomarkers at a later date.

A member of the research team will approach the patient after [name] has introduced the study and the patient agrees to learn more. Once informed consent has been achieved, patients will be randomly placed into one of two groups that will indicate which type of laser lithotripsy they will receive:

- 1) Hol:YAG laser
- 2) Thulium laser

1.3 SCHEDULE OF ACTIVITIES

After randomization, the patient will undergo URS using either the Thulium or Hol:YAG laser. Both lasers are used as part of the standard of care and are used interchangeably. At the beginning of all procedures, the surgeon will empty the bladder and collect a 2 mL sample of urine that will serve as the “Preoperative Urine Sample”. It is the standard of care to collect urine at the beginning of the surgery to send to pathology. The only deviation is that a portion of the urine will be for research. One hour following the end of the procedure, a member of [name] research team will collect a second 2 mL sample of urine that will serve as the “Immediate Post-Op Urine Sample”. This will be collected using the catheter that was placed during surgery. If no catheter was placedb the patient will provide the urine sample.

After collection, the samples will be subsequently frozen in a freezer at -80 °C freezer operated by the pathology department at Mount Sinai West hospital.

A third and final sample of urine will be collected at the patients’ 10-day follow up appointment for stent removal which will serve as the “Follow-up Urine Sample”. To standardize the duration in which the last urine samples are collected, only patients who have been stented will be included in the study, as standard of care for stent removal is ten days. Upon receiving the third and final specimen 10 days postoperatively, the subject’s enrollment will be considered complete. All procedures and appointments are the standard of care.

After sufficient patient enrollment and specimen collection, all the samples will be analyzed for kidney and urothelial injury biomarkers using urinary assays (ELISA, CLIA, etc.). The biomarkers that will be qualified and quantified in the urine include Cystatin C, Kidney Injury Molecule-1 (KIM-1), Neutrophil gelatinase-associated lipocalin (NGAL), Beta-2-microglobulin, Microalbumin urine, spot creatinine, total protein, and glycosaminoglycans.

2 INTRODUCTION

2.1 STUDY RATIONALE

State the problem or question (e.g., describe the population, disease, current standard of care, if one exists, and limitations of knowledge or available therapy), the reason for conducting the clinical trial and the rationale underlying the intervention. State the name and the nature of the intervention, the hypothesized target(s) of the intervention (i.e., the putative cognitive, affective, behavioral, social, community,

organizational, etc., target necessary to produce the behavior change relevant to the clinical outcome), and the clinical outcome of interest.

Standard operations used for the surgical removal of kidney stones include ureteroscopic laser lithotripsy (URS) and percutaneous nephrolithotomy (PCNL). In recent years new modalities have been introduced to both URS and PCNL including new laser technologies such as the Thulium laser and antiretropulsion properties with Holmium lasers (Moses technology). While the overall safety and efficacy of these procedures has been well established, these relatively new modalities have yet to be rigorously studied for potential deleterious effects on the kidney. To date, several studies have attempted to use these biomarkers to determine degree of tissue injury after kidney stone operations, however these studies have been limited by small cohorts and lack of data regarding the newest energy modalities and surgical techniques [1-6]. This study is intended to determine whether different intraoperative variables (type of laser, patient positioning, renal pelvis pressure) correlate with renal damage, as measured by urinary biomarkers.

2.2 BACKGROUND

Nephrolithiasis is one of the most common urologic conditions with a lifetime incidence in the United States approaching 10% and rising [7]. While many kidney stones will pass spontaneously, a significant portion ultimately require surgical intervention in the form of ureteroscopic laser lithotripsy (URS), percutaneous nephrolithotomy (PCNL), or shock wave lithotripsy (SWL) to eradicate the stone burden. The ideal surgical procedure for eradication of kidney stones would have maximal efficiency in stone removal while minimizing collateral damage to the renal parenchyma and the epithelial lining of the collecting system (urothelium). While much is known about the physical properties of stone fragmentation techniques, relatively little is known about the unwanted effect these techniques may have on renal tubular and urothelial cells.

In daily practice, clinicians almost exclusively use a patient's estimated glomerular filtration rate (eGFR), obtained by measuring serum creatinine as a biomarker of renal parenchymal injury. The drawbacks of using serum creatinine as a surrogate for renal function are well known. First, serum creatinine can change with many confounding variables that are unrelated to kidney function such as diet, hydration status, and muscle mass to name a few. More importantly, serum creatinine (eGFR) is considered more a measure of global renal function and has a poor sensitivity for detecting early or small insults to renal tubular cells. In other words, eGFR does not change in any detectable way until a relatively large insult to the kidney has taken place. Lastly, eGFR is a better measure of renal blood flow and is not a direct marker of cellular injury. In recent years, several urinary protein biomarkers have been found that are now known to be markers of renal cellular injury. When compared to eGFR, these markers can detect renal insults earlier and have significantly higher sensitivity. Indeed, they can be used as early predictors of impending acute kidney injury (AKI) [8].

Kidney stone removal operations such as URS involve a number of modifiable factors which may contribute to the degree of renal or urothelial injury. The goal of this study is to use sensitive urinary biomarkers to determine which aspects of URS are associated with the greatest degree of injury to renal tubular cells and urothelium. In this study, we will quantify urinary biomarkers specific for kidney and urothelial injury before and after URS and correlate these markers to different intraoperative variables. We postulate that our results will shed a new light on urological endoscopic procedures.

2.3 RISK/BENEFIT ASSESSMENT

2.3.1 KNOWN POTENTIAL RISKS

There will be no risks to physical harm of the subjects due to study interventions. Both lasers are used interchangeably during URS for kidney stones. The only other intervention performed solely for the purpose of the study is collection of postoperative urine samples. Pre-operative urine samples and follow up urine samples are routinely collected from [name] surgical patients. Surgical intervention and follow up for kidney stones will be performed regardless of a patient's willingness to participate in this study according to the standard of care. Since we will be storing patient samples and data, there is a small risk that personal data will be compromised. This risk will be mitigated by encryption of all data storage devices and use of unique numerical patient identifiers, which will be separately linked to the patient's protected health information.

2.3.2 KNOWN POTENTIAL BENEFITS

There are no potential benefits to participants.

2.3.3 ASSESSMENT OF POTENTIAL RISKS AND BENEFITS

Other than the extremely small risk of compromising protected health information, we do not foresee any risks or benefits to participants in this study. The extent of participation for each subject involves collection of three perioperative urine samples (collected via cystoscope, Foley catheter, or clean void). No invasive procedure will be performed to collect the samples (for example, a Foley catheter will not be placed solely for the purpose of collecting a urine sample for this study).

OBJECTIVES AND ENDPOINTS

OBJECTIVES	ENDPOINTS	JUSTIFICATION FOR ENDPOINTS	PUTATIVE MECHANISMS OF ACTION
Primary			

OBJECTIVES	ENDPOINTS	JUSTIFICATION FOR ENDPOINTS	PUTATIVE MECHANISMS OF ACTION
1) To determine if during ureteroscopic laser lithotripsy, laser type (Ho:Yag Moses 2.0 vs Thulium Fiber Laser) predicts differences in renal-damage associated biomarkers	1) Determination of association between type of laser used during URS and degree of renal damage (as measured by urinary biomarkers).	Quantification of the concentrations of specific urinary biomarkers will allow us to compare the relative tissue damage caused by each laser type.	N/A
Secondary			
To determine if any additional operative factors (i.e. operative time, patient positioning, use of pressurized irrigation, use of a ureteral access sheath) predict differences in levels of renal-damage associated biomarkers.	The secondary endpoint will be determination of association between additional operative variables (see secondary objective) and renal damage during URS.	Quantification of the concentrations of specific urinary biomarkers will allow us to compare the relative tissue damage caused by different variables during URS.	N/A

3 STUDY DESIGN

3.1 OVERALL DESIGN

The overall design is to evaluate the degree of renal damage caused by different laser energy modalities and access sheath calibers used during URS. Pre- and postoperative urine samples will be collected from subjects to quantify urinary biomarkers which are specific for renal damage.

Subjects enrolled will be randomized into two arms, one in which subjects will undergo laser lithotripsy with the Thulium fiber laser (TFL), and the other in which the procedure will be performed with the Holmium:YAG laser.

3.2 SCIENTIFIC RATIONALE FOR STUDY DESIGN

Randomization by laser type is being performed. We chose to do this as this would eliminate any potential bias on the part of the surgeon for preference of one laser type over another. Both lasers are used interchangeable during URS for kidney stones, and surgeons do not typically choose a specific laser to use prior to surgery. We believe that from the subjects' standpoint, there is little to no perceived difference in use of TFL or Ho:YAG lasers, and both are used interchangeably as standard of care.

3.3 JUSTIFICATION FOR INTERVENTION

Surgical interventions for kidney stones will be performed regardless of participation in this study.

3.4 END-OF-STUDY DEFINITION

This investigation will finish once all urine samples have been collected and analyzed for urinary biomarkers for both surgical cohorts.

4 STUDY POPULATION

4.1 INCLUSION CRITERIA

Inclusion Criteria:

- Age \geq 18 years
- Solitary kidney stone within the ureter or kidney $< 2\text{cm}$
- Scheduled to undergo URS with [name]

4.2 EXCLUSION CRITERIA

-Exclusion Criteria:

- Multiple or bilateral renal/ureteral stones
- Staghorn calculi
- History of chronic kidney disease or ESRD
- Presence of indwelling ureteral stent or nephrostomy tube at time of recruitment
- Urinary tract infection (cystitis or pyelonephritis) within 2 weeks of recruitment
- Development of postoperative septic shock (defined as persistent need for pressors > 1 hour after end of procedure)
- Documented ureteral/renal pelvis perforation

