5 STUDY INTERVENTION(S) OR EXPERIMENTAL MANIPULATION(S)

5.1 STUDY INTERVENTION(S) OR EXPERIMENTAL MANIPULATION(S) ADMINISTRATION

5.1.1 STUDY INTERVENTION OR EXPERIMENTAL MANIPULATION DESCRIPTION

For subjects receiving URS, randomization will occur preoperatively. These subjects will be randomized to undergo lithotripsy with either Ho:YAG or TFL lasers (100 subjects in each arm).

All subjects will undergo surgical interventions that abide by broadly accepted guidelines and standards of care, allowing for slight variations in technique as seen necessary by the attending surgeon [name].

The type of laser that is chosen in SOC is based on hospital availability. That is, most hospitals only have one laser type to choose from (and that laser type is generally contingent on the biomedical contracts the hospital holds with the various laser manufacturers). We are uniquely situated at Mount Sinai West in that we have multiple laser systems to choose from. Multiple surgeons share the lasers, and typically [name] will use whichever laser is already in the room or readily available. Approximately 50% of ureteroscopies were performed with each laser, +/- 10%.

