6.2 PARTICIPANT DISCONTINUATION/WITHDRAWAL FROM THE STUDY

Patients will be considered enrolled in the study once consent has been signed. Participants may discontinue or withdraw from the study for any reason and at any point in time through the conclusion of the study. If a participant desires withdrawal after some or all of their urine samples have been collected or analyzed, their urine samples will be discarded in a biohazard-safe and anonymous fashion.

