8.2 SAMPLE SIZE DETERMINATION

A sample size of 108 patients will be accrued locally. We are enrolling 108 patients to allow for any potential exclusions due to failure to follow up or for patients who were not stented.

A study by Fahmy et al. prospectively evaluated urinary Kidney Injury Marker-1 (uKIM-1) levels in patients undergoing kidney stone surgery to compare the effect of Extracorporeal Shockwave Lithotripsy (ESWL) and Ureteroscopy/Laser Lithotripsy (URS) on biomarkers of renal damage¹. In this study, the 50 patients in the ESWL arm had a mean preoperative uKIM-1 of 5.78ng/mL (SE=0.8) and the 10 patients in the URS arm similarly had a mean preoperative uKIM-1 of 5.78ng/mL (SE=2.0). Two hours post operatively, the ESWL group had a mean uKIM1 of 10.14ng/mL (SE=1.4) and the URS group had a uKIM-1 of 5.49ng/mL (SE 0.7, SD=2.21). Another study by Timmeren et al evaluated uKIM1 in 11 health controls and 53 patients with varying degrees of kidney disease and found a -0.37 correlation ($p=0.016$) between uKIM-1 levels and eGFR.² That is, a 1ng/mL rise in uKIM1 correlated to a 0.37mL/min decline in eGFR. The purpose of our statistical analysis is to evaluate for non-inferiority of the two laser modalities in regard to occult kidney damage. Given that kidney stone disease is a recurrent illness often requiring multiple surgical interventions over the course of a patient's lifetime, we defined non-inferiority as producing a change in eGFR 1mg/mL. With an allocation ratio of 1:1, 99% power, non-inferiority limit of 40%, and alpha of 5%, using the noninferiority power calculation, our sample size is 49 patients in each study arm for 98 patients in total (~100). Based on these calculations and factoring in a 10% dropout rate, we seek to enroll 108 total patients.

Power Calculation References

2. van Timmeren MM, van den Heuvel MC, Bailly V, Bakker SJ, van Goor H, Stegeman CA. Tubular kidney injury molecule-1 (KIM-1) in human renal disease. *The Journal of pathology*. 2007;212(2):209-217.

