8.3 POPULATIONS FOR ANALYSES

All enrolled subjects will be included for analyses.

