8.4.2 ANALYSIS OF THE PRIMARY ENDPOINT(S)

Abundance of each kidney injury biomarker for each laser will be analyzed using the Kruskal-Wallis statistical test. Multiple multivariate regression will also be used to control for stone size, operative time, and other potential confounders.

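### Section 4.2 excludes patients for postoperative septic shock, which can only follow randomisation, while 8.3 analyses everyone enrolled; the plan should say which rule holds

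*Combined protocol and SAP*

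**What the plan says.** Section 4.2 ends its list of exclusions with two items that differ in kind from the rest: "Development of postoperative septic shock (defined as persistent need for pressors > 1 hour after end of procedure" and "Documented ureteral/renal pelvis perforation". The first is defined by what happens after the operation. The second has no stated timing.

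On the order of events, 5.1.1 says "For subjects receiving URS, randomization will occur preoperatively", and 5.3 adds that the list of IDs is randomised before the study starts. Section 6.2 says "Patients will be considered enrolled in the study once consent has been signed". Section 8.3 is a single sentence: "All enrolled subjects will be included for analyses". The primary analysis in 8.4.2 is "Abundance of each kidney injury biomarker for each laser will be analyzed using the Kruskal-Wallis statistical test", supplemented by regression.

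Three other places bear on who is analysed. Section 8.2 says "We are enrolling 108 patients to allow for any potential exclusions due to failure to follow up or for patients who were not stented". Section 1.3 limits the study to patients who received a stent. Section 6.3 automatically withdraws patients who miss the stent-removal visit and discards their samples.

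**The concern.** A patient who consents, is randomised, has surgery and then develops septic shock is out under 4.2 and in under 8.3. No sentence says which rule prevails, so the choice could be made after the data are seen.

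The direction of risk is clear. Septic shock, or a perforation made during ureteroscopy, may be related to the laser. If such patients are dropped, the randomised arms are compared only among those without overt injury. The most injured patients may be missing, possibly in unequal numbers. Section 8 plans no count of these patients by laser, so a reader of the results might not learn how many each arm lost. The synopsis speaks of determining a safety profile, and a finding of similar biomarker levels would be read in that light.

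**Working it through.** **1. Timing, section against section.**
- Septic shock: assignment is preoperative (5.1.1), and the definition needs pressors for more than one hour after the procedure ends (4.2). It always falls after randomisation.
- Perforation: 4.2 gives no timing. One that occurs during ureteroscopy falls after randomisation; one already present need not.
- Enrolment is at consent (6.2), so both kinds of patient are already in the 8.3 population.

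**2. Can 8.3 be assumed to prevail?** No. Section 8.2 expects some enrolled patients to be left out, but the reasons it names are lost follow-up and no stent, not these two events.

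**3. Does missing data explain the exclusion?** Only in part. Section 1.3 says "One hour following the end of the procedure, a member of [name] research team will collect a second 2 mL sample of urine", which is due no later than the moment at which the septic-shock definition can be met. The preoperative and one-hour samples should therefore usually exist. The 10-day sample may not.

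**4. The plan's own allowance.** 98 × 1.10 = 107.8, or 108 as stated (98 / 0.90 = 108.9 would give 109). The allowance is 108 − 98 = 10 patients.

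**5. How many patients.** The documents give no complication rate, so the combined rate p is assumed. Expected number = 108p; chance of at least one = 1 − (1 − p)^108.

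| Assumed p | Expected of 108 | Chance of at least one |
|---|---|---|
| 1% | 1.1 | 66% |
| 2% | 2.2 | 89% |
| 5% | 5.4 | 99.6% |

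**6. Effect on the rank test.** Assume 54 per arm (108 from 8.2, split equally). Let k patients in arm A hold the highest values, with the arms otherwise alike. With those patients kept, P(A > B) = k/54 + 0.5 × (54 − k)/54; with them removed it is 0.500. The null standard error is sqrt(109 / (12 × 54 × 54)) = 0.0558.

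| Removed, A vs B | P(A > B) if kept | Shift on removal | In null SE |
|---|---|---|---|
| 1 vs 0 | 0.509 | 0.009 | 0.17 |
| 2 vs 0 | 0.519 | 0.019 | 0.33 |
| 5 vs 0 | 0.546 | 0.046 | 0.83 |

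**7. Effect on the mean.** Shift = (k/54) × m × 2.21 ng/mL, where 2.21 is the post-ureteroscopy SD in 8.2 and m is an assumed excess of 1 to 3 SD. For k = 1 this is 0.04 to 0.12 ng/mL; for k = 5 it is 0.20 to 0.61. If the 40% limit means 40% of the 5.49 ng/mL mean in 8.2 (it does not say), the limit is 0.40 × 5.49 = 2.2 ng/mL. The shifts are then 2% to 6% of it for k = 1 and 9% to 28% for k = 5.

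**8. How likely is the extreme split?** With equal rates in the two arms, the chance of 5 or more against 0 is 2 × P(X ≥ 5) × (1 − p)^54, with X binomial(54, p). At 5% this is 2 × 0.132 × 0.0627 = 1.7%. At 2% it is 0.3%, and at 1% it is 0.02%. Unequal true rates would raise these figures.

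**The case against.** The strongest reply is about size. The larger shifts need about five events, all in one arm; the rank figure also needs all five to hold the highest values. With one or two patients, the effect is slight. That stands, and it is why the point is graded as minor.

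A second reply is clinical: sepsis or perforation may move these markers by itself, so a comparison without such patients has some logic. That supports a sensitivity analysis. It does not support removing randomised patients from the primary comparison because of something that happened after assignment.

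A third reply is that the stented-only rule and the withdrawal of no-shows are the bigger conflict with 8.3, since they are the losses for which 8.2 budgets about 10 patients. That stands too. A repair limited to 4.2 and 8.3 would only move the contradiction.

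A reader might also infer that overt harm goes unrecorded or is being hidden. The documents do not support this. Adverse events are monitored in all enrolled subjects (7.1.3) and entered on the eCRF (7.1.4, 9.1.3.1), and counts by arm could be drawn from those data. What is absent is a commitment to report them by laser. Nor would an imbalance in overt events make the stated claim false, because 8.2 limits it to occult damage.

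**Conclusion.** The contradiction is real and certain for septic shock. For perforation it holds only if the event occurs during or after ureteroscopy, which is a plausible reading of 4.2 but not a stated one. It would be too strong to say that every perforation exclusion follows randomisation, or that the plan definitely drops these patients: 8.3 says the opposite, and the fault is that the two rules are left unreconciled.

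It would also be too strong to say that the biomarker comparison is invalid. A removal of 5 versus 0 shifts the rank statistic by 0.83 null standard errors, which cannot create or hide a significant result by itself and could matter only where a trend already exists. A 1 versus 0 removal shifts it by 0.17. These sizes rest on assumed rates of 1% to 5%, 54 patients per arm, and affected patients holding the highest values. The expected effect is minor, but at those rates at least one such patient is more likely than not, so the rule should be settled before results are known.

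**What to change.** 1. In 4.2, keep only criteria that can be known before randomisation.
2. In 8.3, state that septic shock, and perforation during or after ureteroscopy, do not remove a patient from the primary comparison. Analyse these patients by assigned laser with whatever samples they have.
3. In 8.4, add one sensitivity analysis without these patients, and report the number affected in each arm.
4. In the same clarification, say how the stented-only rule (1.3) and the withdrawal of no-shows with samples discarded (6.3) fit with 8.3. Preferably, keep the preoperative and one-hour samples of no-shows where consent allows. The wording of 8.2 on expected exclusions should then match.

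A wider table of adverse and serious adverse events by laser would be a useful addition from data already collected, but is optional.

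The cost is a few sentences across 1.3, 4.2, 6.3, 8.2, 8.3 and 8.4, with no new visits or patients. For septic shock and perforation, it means assays on already scheduled samples from about 1 to 5 patients at the assumed rates; keeping no-shows' samples would add some more. The downside is that the retained patients may add noise to the markers and may lack the 10-day sample; the sensitivity analysis shows how much their inclusion matters.
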